2.3 POTENTIAL RISKS AND BENEFITS

2.3.1 KNOWN POTENTIAL RISKS

A. Ibrutinib

As previously described, ibrutinib is approved for the treatment of patients with relapsed/refractory CLL and patients with CLL with del 17p. The most common adverse events ($\geq 20\%$) in patients with CLL treated with ibrutinib are neutropenia, thrombocytopenia, diarrhea, anemia, fatigue, upper respiratory infection, skin rashes, nausea and pyrexia (see IMBRUVICA package insert for most current and full listing of possible risks).

- **Hemorrhage**: Fatal bleeding events have occurred in patients treated with ibrutinib. Grade 3 or higher bleeding events (intracranial hemorrhage [including subdural hematoma], gastrointestinal bleeding, hematuria, and post procedural hemorrhage) have occurred in 3% of patients, with fatalities occurring in 0.3% of patients in clinical trials. Bleeding events of any grade, including bruising and petechiae, occurred in 44% of patients treated with ibrutinib. The mechanism for the bleeding events is not well understood.
 - For any planned surgery or invasive procedure requiring sutures or staples for closure, ibrutinib should be held at least 7 days prior to the intervention and should be held at least 7 days after the procedure, and restarted at the discretion of the investigator when the surgical site is reasonably healed without serosanguinous drainage or the need for drainage tubes.
 - For planned minor procedures (such as a central line placement, needle biopsy, thoracentesis, or paracentesis) ibrutinib should be held for at least 3 days prior to the procedure and should not be restarted for at least 3 days after the procedure. For bone marrow biopsies that are performed while the subject is on ibrutinib, it is not necessary to hold ibrutinib for these procedures.
 - For emergency procedures, ibrutinib should be held after the procedure until the surgical site is reasonably healed, for at least 7 days after the urgent surgical procedure, or at the discretion of the investigator.
- **Infections**: Fatal and non-fatal infections have occurred with ibrutinib therapy. Grade 3 or greater infections occurred in 24% of patients in clinical trials. Cases of progressive multifocal leukoencephalopathy (PML) and *Pneumocystis jirovecii* pneumonia (PJP) have occurred in patients treated with ibrutinib. Evaluate patients for fever and infections and treat appropriately per current guidelines. Prophylaxis according to standard of care should be considered in patients who are at increased risk for opportunistic infections.
- **Cytopenias**: Treatment-emergent Grade 3 or 4 cytopenias including neutropenia (24%), thrombocytopenia (range, 8%), and anemia (3%) based on laboratory measurements occurred in patients treated with single agent ibrutinib. Monitor complete blood counts at least monthly.
- **Cardiac Arrhythmias**: Fatal and serious cardiac arrhythmias have occurred with ibrutinib therapy. Grade 3 or greater ventricular tachyarrhythmias occurred in 0.2% of patients, and Grade 3 or greater atrial fibrillation and atrial flutter occurred in 4% of patients. These events have occurred particularly in patients with cardiac risk factors, hypertension, acute infections, and a previous history of cardiac arrhythmias. Periodically monitor patients clinically for cardiac arrhythmias. Obtain an ECG for patients who develop arrhythmic symptoms (e.g., palpitations, lightheadedness, syncope, chest pain) or new onset dyspnea. Manage cardiac arrhythmias appropriately, and if it persists, consider the risks and benefits of ibrutinib treatment and follow dose modification guidelines.
- **Hypertension**: Hypertension (range, 12%) has occurred in patients treated with ibrutinib with a median time to onset of 5 months (range, 0.03 to 22 months). Monitor patients for new onset hypertension or hypertension that is not adequately controlled after starting ibrutinib. Adjust existing anti-hypertensive medications and/or initiate anti-hypertensive treatment as appropriate.
- **Second Primary Malignancies**: Other malignancies (9%) including non-skin carcinomas (2%) have occurred in patients treated with ibrutinib. The most frequent second primary malignancy was non-melanoma skin cancer (6%).

- **Tumor Lysis Syndrome**: Tumor lysis syndrome has been infrequently reported with ibrutinib therapy. Assess the baseline risk (e.g., high tumor burden) and take appropriate precautions. Monitor patients closely and treat as appropriate.
- **Embryo-Fetal Toxicity**: Based on findings in animals, ibrutinib can cause fetal harm when administered to a pregnant woman. Administration of ibrutinib to pregnant rats and rabbits during the period of organogenesis caused embryo-fetal toxicity including malformations at exposures that were 2-20 times higher than those reported in patients with MCL, CLL/SLL or WM. Advise women to avoid becoming pregnant while taking ibrutinib and for 1 month after cessation of therapy. If this drug is used during pregnancy or if the patient becomes pregnant while taking this drug, the patient should be apprised of the potential hazard to a fetus.

B. Pembrolizumab

Pembrolizumab does not have a current indication for CLL. It is currently approved for unresectable or metastatic melanoma, metastatic NSCLC, metastatic HNSCC and refractory Hodgkin lymphoma. Most adverse reactions ($\geq 20\%$ of patients) were consistent with fatigue, pruritus, decreased appetite, skin rash, pyrexia, cough, dyspnea, musculoskeletal pain, constipation and nausea (KEYTRUDA package insert). Of clinical importance are the immune-related adverse events:

- **Immune mediated pneumonitis**: Pneumonitis occurred in 94 (3.4%) of 2799 patients receiving pembrolizumab, including grade 1 (0.8%), grade 2 (1.3%), grade 3 (0.9%), grade 4 (0.3%), and grade 5 (0.1%) pneumonitis. The median time to onset was 3.3 months (range: 2 days to 19.3 months), and the median duration was 1.5 months (range: 1 day to 17.2+ months). Sixty-three (67%) of the 94 patients received systemic corticosteroids, with 50 of the 63 receiving high-dose corticosteroids for a median duration of 8 days (range: 1 day to 10.1 months) followed by a corticosteroid taper. Pneumonitis occurred more frequently in patients with a history of prior thoracic radiation (6.9%) than in patients who did not receive prior thoracic radiation (2.9%). Pneumonitis led to discontinuation of pembrolizumab in 36 (1.3%) patients. Pneumonitis resolved in 55 (59%) of the 94 patients.
- **Immune-mediated colitis**: Colitis occurred in 48 (1.7%) of 2799 patients receiving pembrolizumab, including grade 2 (0.4%), grade 3 (1.1%), and grade 4 ($<0.1\%$) colitis. The median time to onset was 3.5 months (range: 10 days to 16.2 months), and the median duration was 1.3 months (range: 1 day to 8.7+ months). Thirty-three (69%) of the 48 patients received systemic corticosteroids, with 27 of the 33 requiring high-dose corticosteroids for a median duration of 7 days (range: 1 day to 5.3 months) followed by a corticosteroid taper. Colitis led to discontinuation of pembrolizumab in 15 (0.5%) patients. Colitis resolved in 41 (85%) of the 48 patients.
- **Immune-mediated hepatitis**: Hepatitis occurred in 19 (0.7%) of 2799 patients receiving pembrolizumab, including grade 2 (0.1%), grade 3 (0.4%), and grade 4 ($<0.1\%$) hepatitis. The median time to onset was 1.3 months (range: 8 days to 21.4 months), and the median duration was 1.8 months (range: 8 days to 20.9+ months). Thirteen (68%) of the 19 patients received systemic corticosteroids, with 12 of the 13 receiving high-dose corticosteroids for a median duration of 5 days (range: 1 to 26 days) followed by a corticosteroid taper. Hepatitis led to discontinuation of pembrolizumab in 6 (0.2%) patients. Hepatitis resolved in 15 (79%) of the 19 patients.
- **Immune mediated endocrinopathies**: Hypophysitis occurred in 17 (0.6%) of 2799 patients receiving pembrolizumab, including grade 2 (0.2%), grade 3 (0.3%), and grade 4 ($<0.1\%$) hypophysitis. The median time to onset was 3.7 months (range: 1 day to 11.9 months), and the median duration was 4.7 months (range: 8+ days to 12.7+ months). Sixteen (94%) of the 17 patients received systemic corticosteroids, with 6 of the 16 receiving high-dose corticosteroids. Hypophysitis led to discontinuation of pembrolizumab in 4 (0.1%) patients. Hypophysitis resolved in 7 (41%) of the 17 patients.
- **Thyroid disorders**: Hyperthyroidism occurred in 96 (3.4%) of 2799 patients receiving pembrolizumab, including grade 2 (0.8%) and grade 3 (0.1%) hyperthyroidism. The median time to onset was 1.4 months (range: 1 day to 21.9 months), and the median duration was 2.1 months (range: 3 days to 15.0+ months). Hyperthyroidism led to discontinuation of pembrolizumab in 2 ($<0.1\%$) patients. Hyperthyroidism resolved in 71 (74%) of the 96 patients. Hypothyroidism

occurred in 237 (8.5%) of 2799 patients receiving pembrolizumab, including grade 2 (6.2%) and grade 3 (0.1%) hypothyroidism. The median time to onset was 3.5 months (range: 1 day to 18.9 months), and the median duration was not reached (range: 2 days to 27.7+ months). Hypothyroidism led to discontinuation of pembrolizumab in 1 (<0.1%) patient. Hypothyroidism resolved in 48 (20%) of the 237 patients. The incidence of new or worsening hypothyroidism was higher in patients with HNSCC occurring in 28 (15%) of 192 patients receiving pembrolizumab, including grade 3 (0.5%) hypothyroidism. Of these 28 patients, 15 had no prior history of hypothyroidism. Thyroiditis occurred in 16 (0.6%) of 2799 patients receiving pembrolizumab, including Grade 2 (0.3%) thyroiditis. The median time of onset was 1.2 months (range: 0.5 to 3.5 months).

- **Immune-mediated Nephritis and renal dysfunction:** Nephritis occurred in 9 (0.3%) of 2799 patients receiving pembrolizumab, including grade 2 (0.1%), grade 3 (0.1%), and grade 4 (<0.1%) nephritis. The median time to onset was 5.1 months (range: 12 days to 12.8 months), and the median duration was 3.3 months (range: 12 days to 8.9+ months). Eight (89%) of the 9 patients received systemic corticosteroids, with 7 of the 8 receiving high-dose corticosteroids for a median duration of 15 days (range: 3 days to 4.0 months) followed by a corticosteroid taper. Nephritis led to discontinuation of pembrolizumab in 3 (0.1%) patients. Nephritis resolved in 5 (56%) of the 9 patients
- **Infusion-related reactions:** Acute infusion reactions (which can include cytokine release syndrome, angioedema, or anaphylaxis) are different from allergic/hypersensitive reactions, although some of the manifestations are common to both AEs. Signs and symptoms usually develop during or shortly after drug infusion and generally resolve completely within 24 hours of completion of infusion. Signs/symptoms may include: Allergic reaction/hypersensitivity (including drug fever); Arthralgia (joint pain); Bronchospasm; Cough; Dizziness; Dyspnea (shortness of breath); Fatigue (asthenia, lethargy, malaise); Headache; Hypertension; Hypotension; Myalgia (muscle pain); Nausea; Pruritis/itching; Rash/desquamation; Rigors/chills; Sweating (diaphoresis); Tachycardia; Tumor pain (onset or exacerbation of tumor pain due to treatment); Urticaria (hives, welts, wheals); Vomiting. Pembrolizumab can cause severe or life-threatening infusion-related reactions and has been reported in 6 (0.2%) out of 2799 patients that received the drug.
- **Embryo-fetal toxicity:** Based on its mechanism of action, pembrolizumab can cause fetal harm when administered to a pregnant woman. Animal models link the PD-1/PD-L1 signaling pathway with maintenance of pregnancy through induction of maternal immune tolerance to fetal tissue. If this drug is used during pregnancy, or if the patient becomes pregnant while taking this drug, apprise the patient of the potential hazard to a fetus. Advise females of reproductive potential to use highly effective contraception during treatment with pembrolizumab and for 4 months after the last dose of the drug.
- **Immunogenicity:** As with all therapeutic proteins, there is the potential for immunogenicity. Trough levels of pembrolizumab interfere with the electrochemiluminescent (ECL) assay results; therefore, a subset analysis was performed in the patients with a concentration of pembrolizumab below the drug tolerance level of the anti-product antibody assay. In clinical studies in patients treated with pembrolizumab at a dose of 2 mg/kg every 3 weeks, 200 mg every 3 weeks, or 10 mg/kg every two or three weeks, 26 (2.0%) of 1289 evaluable patients tested positive for treatment-emergent anti-pembrolizumab antibodies. Among the 26 patients who tested positive for treatment emergent anti-pembrolizumab antibodies, only 4 patients were tested for neutralizing antibodies and one was positive. There was no evidence of an altered pharmacokinetic profile or increased infusion reactions with anti-pembrolizumab binding antibody development. The detection of antibody formation is highly dependent on the sensitivity and specificity of the assay. Additionally, the observed incidence of antibody (including neutralizing antibody) positivity in an assay may be influenced by several factors including assay methodology, sample handling, timing of sample collection, concomitant medications, and underlying disease. For these reasons, comparison of incidence of antibodies to pembrolizumab with the incidences of antibodies to other products may be misleading.

2.3.2 KNOWN POTENTIAL BENEFITS

In February 2014, ibrutinib was the first BTK inhibitor FDA approved for clinical use for the treatment of patients with CLL who had relapsed after at least one prior line of therapy or presence of 17p deletion. The indication was extended to patients with CLL 17p deletion as first line therapy and patients unfit for chemotherapy (older than 65 years old). Ibrutinib has received full approval for use in CLL/SLL.

Pembrolizumab is currently approved for metastatic/advanced melanoma, recurrent or metastatic NSCLC, recurrent or metastatic HNSCC and refractory classical Hodgkin Lymphoma. Pembrolizumab does not have current approval for CLL at this time. However activity of pembrolizumab has been documented in CLL and Richter's transformation with overall clinical responses and minimal toxicity.

As mentioned in the rationale, there is an opportunity of the drug combination to correct the immune dysfunction typical of patients with CLL. Restoration of immune function could lead to improvement of the antitumor response and immunity against infections. In addition, treating high risk CLL early may have beneficial effects on long term survival.

3 OBJECTIVES AND PURPOSE

Objective:

This is designed as a phase II study intended to evaluate the impact of sequential overlapping treatment with PD-1 monoclonal antibody (mAb), pembrolizumab/MK-1375, followed by ibrutinib on endogenous immune function in previously untreated, high-risk CLL patients (defined as presence of del17p or TP53, del11q or ATM mutation, unmutated IGVH or mutated IGVH with 3.21 phenotype) with absolute lymphocyte count >20,000 but without meeting iwCLL criteria to start therapy.

Primary Objectives:

1. Assessment of the complete response (CR) of CLL to therapeutic intervention (defined per current iWCLL 2008 response criteria)
2. Time to response of CLL to therapeutic intervention (defined as time to achievement of response according to iWCLL 2008 criteria).

Secondary Objectives

1. Assessment of the overall response rate (ORR) [CR + PR] per iWCLL 2008 response criteria
2. Restoration of immune response as measured by:
 - a. Decreased markers of T-cell exhaustion
 - b. Increased of quantitative immunoglobulin levels and subtype
2. Safety and toxicity of the combination
3. Progression free survival (PFS)
4. 3. Incidence of Richter's transformation (defined as transformation of CLL into an aggressive lymphoid/histiocytic histology including well defined World Health Organization 2008 subtypes). Richter's transformation should be biopsy proven

Exploratory Objectives:

1. Alterations in T lymphocyte function, including changes in:
 - a. TH1:TH2 polarization, and TReg:TH17 distributions
 - b. Markers of T cell exhaustion and/or inhibition
 - c. Alterations in distribution of naïve vs. memory
 - d. Cellular activation and cell-mediated cytotoxic capacity
2. Alterations in B lymphocyte function, including changes in:
 - a. Serum anti-pneumococcal antibody titers in response to Prevnar vaccination
 - b. Quantitative serum immunoglobulin levels and subtyping
 - c. Fc-receptor (FcR) expression patterns
3. Alterations in global systemic cytokine patterns: Includes IFN- γ , TNF- α , IL-2, IL-4, IL-10, IL-6, IL-17A, allowing discrimination between TH1, TH2, and TH17 profiles (described in Section 4.2.2.2)

Hypothesis for Primary and Secondary Objectives:

The therapeutic combination of PD1:PDL1 blockade (PDB) and ibrutinib can improve the severe immune dysfunction classically associated with CLL, thereby improving disease-related morbidity and mortality in high-risk, previously untreated patients.

- A. The combination of PDB and ibrutinib will reverse T cell dysfunction commonly seen in CLL patients, potentiating more robust anti-infective and anti-tumor immune responses.
- B. The combination of PDB and ibrutinib will restore protective humoral responses in CLL patients. In particular, immunologic restoration will improve responses and protection against pneumococcal infection which represent a significant cause of morbidity and mortality.
- C. The combination of PDB and ibrutinib can have a synergistic effect on the response rate.

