4 STUDY DESIGN AND ENDPOINTS

4.1 DESCRIPTION OF THE STUDY DESIGN

Trial Design

The trial is an open-label, single arm phase II study to be conducted only at the Moffitt Cancer Center. Anticipated accrual will be 25 subjects. One of the secondary endpoint of this study is reconstitution of immune function, using response to pneumococcal vaccination as a clinical surrogate representation of global immune function. The study is designed to test the null hypothesis that, in high risk CLL (defined as presence of del17p or TP53, del11q or ATM mutation, unmutated IGVH or mutated IGVH with 3.21 phenotype) patients who do not require treatment of CLL and receive PD-1:PD-L1 blockade along with ibrutinib, challenge with the 7-valent pneumococcal vaccine will elicit an immunologic response <40%, defined as the generation of detectable antibody responses to >6 antigens. Our specified alternative hypothesis is that vaccination in the context of PD-1 blockade and ibrutinib will elicit an immunologic response >60% with 90% power.

Overall treatment Schema: All intravenous treatments will be administered at the outpatient Moffitt Cancer Center Infusion Center. The patients will receive a combination of IV pembrolizumab (anti-PD1) and oral ibrutinib according to the scheduled depicted in Figure 1. Briefly, patients will receive pembrolizumab on a 3-week interval schedule for a total of at least 51 weeks (it could be extended for up to 2 years if clinical benefit per investigator); starting with week 6, patients will additionally start daily oral ibrutinib which will be continued through 54 weeks of ibrutinib therapy. The rationale of starting pembrolizumab first is to avoid overlapping toxicity of ibrutinib and the anti-PD1 antibody.

Biomarker Research

Immune Monitoring Laboratory Correlates:

1. Global Immune function will be assessed in terms of serum cytokine patterns. Patient sera will be evaluated by flow cytometric means using cytokine bead arrays to measure serum cytokine levels quantitatively. The cytokine panel will include IFN- γ , TNF- α , IL-2, IL-4, IL-10, IL-6, IL-17A, allowing discrimination between TH1, TH2, and TH17 profiles.

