2. T cell function will be assessed for changes in multiple characteristics including memory formation, TH-polarity, markers of exhaustion, and activation via flow cytometric analysis. Naïve and memory subpopulations will be defined according to expression of CD45RA, CD62L, CCR5 and CCR7. TH-polarization, including TH1, TH2, TH17 and TReg subsets, will be determined by intracellular cytokine and FoxP3 profiles. Changes in T cell exhaustion phenotype will be tracked in terms of surface expression of several well-defined markers, including CD160, CD200R, CD244, CD272, CD274, CD279, as well as the intracellular markers Lag3 and Tim3. Alterations in cellular activation will be measured in terms of phosphorylation of critical T cell signaling pathways, STAT 1, 3 and 5, as well as by surface expression of CD107a, correlating to secretory/cytotoxic activity.
3. Humoral immunity will be monitored in terms of quantitative serum immunoglobulin levels as well as IgG subtyping by ELISA assay. FcR subtype utilization patterns will also be evaluated by flow cytometric means to identify potential alterations in cellular interpretation of antibody-mediated signaling.
4. Evaluation of MRD by 4-color flow cytometry. It will be performed in patients who achieved CR and PR per iwCLL criteria. If CBC with differential demonstrates the normalization of WBC to normal limits with no evidence of lymphocytosis, a peripheral blood sample will be obtained (within 14 days) to determine the MRD status of the CLL in peripheral blood by multiparameter flow cytometry. If MRD is negative, a confirmation of MRD status in the bone marrow will be performed at the discretion of the investigator.
5. Peripheral blood to collect DNA and RNA will be stored for future assessments.

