13. Has a known history of Human Immunodeficiency Virus (HIV) (HIV 1/2 antibodies).
14. Has known active Hepatitis B (e.g., HBsAg reactive) or Hepatitis C (e.g., HCV RNA [qualitative] is detected).
15. Has received a live vaccine within 30 days prior to the first dose of trial treatment. Patients who had pneumococcal vaccination within 6 months from starting trial will not be eligible for the study.
16. Major surgery or a wound that has not fully healed within 4 weeks of first dose.
17. History of stroke or intracranial hemorrhage within 6 months prior to first dose.
18. Requires anticoagulation with warfarin or equivalent vitamin K antagonists (eg, phenprocoumon).
19. Requires chronic treatment with strong CYP3A inhibitors.
20. Clinically significant cardiovascular disease such as uncontrolled or symptomatic arrhythmias, congestive heart failure, or myocardial infarction within 6 months of Screening, or any Class 3 (moderate) or Class 4 (severe) cardiac disease as defined by the New York Heart Association Functional Classification.

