7.2 RESEARCH BLOOD SPECIMEN PREPARATION, HANDLING, AND STORAGE

Blood samples for correlative studies will be collected at baseline (prior to first dose of study drug), at week 9, week 12, and end of ibrutinib treatment. Peripheral blood will be utilized with an estimated volume of 50 cc collected in five green top tubes.

1. Preparation of Samples

Whole blood samples in 5 green top tubes (10ml/tube) will be received in the laboratory of [name]. Plasma will be isolated by centrifugation of the green top tubes for 5min at 1500rpm and lymphocyte isolation will be performed using Ficol gradient isolation for the purpose of immune testing.

2. Sample Storage

For storage, plasma will be held in 1.5 ml aliquots and placed in a -20C freezer. Lymphocytes will be frozen using 90% FBS and 10% DMSO and placed in a -80C freezer for short term storage. Long term storage of lymphocytes will be conducted utilizing liquid nitrogen.

3. Long-Term Use of Samples

Any isolated plasma and lymphocytes will be stored for the duration of the trial utilizing the short term method above and will be tested per protocol parameters outlined in Section 4.1. With the subject's permission, any samples remaining at the end of the trial will be placed in long term storage for use in future research. If any subject does not agree, that subject's remaining samples will be destroyed at the final closure of the trial.

4. Procedure for Clinical Trial Staff

The following procedure is recommended to be used for collaboration with the Research Science Lab:

- a. Notify the Research lab at least 2 days prior to the collection, using the template below.
Email to [contact] and cc [contact]
Follow up with a phone message to [name].
- b. Prepare a plastic bag with 5 green top tubes (tubes obtained from [name] lab). Attach label to tubes with MCC #, subject MRN, and date of collection. Each bag will have a label attached with the MCC #, subject MRN, DOB, initials, date/time of collection. Label should have research lab contact information. ("Contact [name] or [contact] for pick-up").
- c. Deliver bag of tubes to the Blood Draw area the day prior to collection.

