¹⁰ Tumor imaging will consist of CT of the neck, chest, abdomen and pelvis that will be performed at screening, if not done within 3 months prior to study entry. Response assessment will be done at week 12, week 24, and end of 51 weeks of treatment. CT scans may be performed at different intervals at investigator discretion (i.e. suspicion of progressive disease). Imaging studies post treatment discontinuation will be performed per investigator discretion (including end of treatment imaging assessment).

¹¹ Bone marrow biopsy will be performed at screening (if not performed within 30 days) and after the end of pembrolizumab and ibrutinib therapy (28-35 days after week 51). If subject discontinues treatment early or progression of disease is suspected, a bone marrow biopsy will be per investigator discretion. During follow-up, bone marrow biopsies will be performed per investigator discretion.

¹² Correlative studies. Please refer to Section 4.1 for biomarkers to be studied. They will be performed at baseline (prior to first dose of study drug), at week 6, week 21, and end of ibrutinib treatment. See Section 7.2 for correlative sample collection procedure. They will be performed at investigator's discretion if early study termination

¹³ Safety follow-up will be 90 days after the end of pembrolizumab treatment (may be at the regularly scheduled monthly visit that is nearest to 90 days if continuing on ibrutinib treatment) and 30 days post discontinuation of ibrutinib treatment. If the subject discontinues early, safety follow up must occur before first dose of the next therapy.

¹⁴ Follow-up after a subject has discontinued trial treatment will be every 12 weeks for 12 months.

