7.7 PROPHYLACTIC MEDICATIONS, TREATMENTS, AND PROCEDURES

Tumor lysis syndrome

It will follow our Moffitt Cancer Center institutional standards for TLS prophylaxis. All patients with high tumor burden (WBC > 25 000 and/or bulky disease [masses or lymphadenopathy greater than 7.5cm) must be treated with allopurinol (or alternative) starting 12 to 24 prior to the first infusion of pembrolizumab. TLS prophylaxis medications may be discontinued at the investigator discretion.

Anti-infectives prophylaxis

If clinically indicated, antiviral, antifungal, antiparasitic (such as *Pneumocystis Jiroveci* pneumonia) and/or antibacterial may be considered but it is not mandated in this study.

Prevnar 13 vaccination

For standard evaluation of immunogenicity the Pneumococcal 13-valent Conjugate Vaccine (Prevnar 13) will be utilized. Patients will receive Prevnar 13 n week 6 day 1 (if not given in the prior 8 weeks). The dose will be the standard 0.5 mg single dose prefilled syringe administered by intramuscular (IM) route

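### The pneumococcal antibody response has a stated hypothesis but no named assay, and the two conflicting sampling schedules each lack half of an early before/after pair

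*Combined protocol and SAP*

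**What the plan says.** **Hypothesis.** Section 4.1 treats vaccine response as the surrogate for a secondary endpoint, immune reconstitution. Its null is that "challenge with the 7-valent pneumococcal vaccine will elicit an immunologic response <40%, defined as the generation of detectable antibody responses to >6 antigens". Its alternative is that "vaccination in the context of PD-1 blockade and ibrutinib will elicit an immunologic response >60% with 90% power".

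**Tier.** Section 3 lists "Serum anti-pneumococcal antibody titers in response to Prevnar vaccination" as exploratory. Section 4.2.2 does not include vaccine response among the secondary endpoints, but 10.1 names the B-cell response to the vaccine alongside the overall response rate as secondary.

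**Assays.** The laboratory list in 4.1 covers a serum cytokine panel, T-cell flow cytometry, humoral tests, minimal residual disease, and stored DNA and RNA. Its humoral item reads "Humoral immunity will be monitored in terms of quantitative serum immunoglobulin levels as well as IgG subtyping by ELISA assay", and adds Fc-receptor patterns by flow cytometry. Section 7.2 says that isolated plasma and lymphocytes "will be tested per protocol parameters outlined in Section 4.1". Footnote 12 of the schedule of events also points to 4.1 for the biomarkers.

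**Vaccination.** Prevnar 13 is given at week 6 (7.3.2.4 and 7.7), with the condition "if not given in the prior 8 weeks". Exclusion criterion 15 reads: "Patients who had pneumococcal vaccination within 6 months from starting trial will not be eligible for the study".

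**Sampling.** Footnote 12 says of the correlative studies: "They will be performed at baseline (prior to first dose of study drug), at week 6, week 21, and end of ibrutinib treatment". Sections 7.1.13 and 7.3.2 agree. Section 7.2 instead gives baseline, week 9, week 12 and end of ibrutinib.

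**Analysis.** Section 10.2.2 covers T-cell exhaustion, immunoglobulin levels and progression-free survival. It has no vaccine-responder analysis.

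**The concern.** A hypothesis about a proportion of vaccine responders needs four things: an assay that can classify each patient, a pre-vaccine value, a post-vaccine value at a useful time, and a rule that turns these into responder or non-responder. Here the assay is not named, the sampling times differ between sections, and the rule counts antigens of a vaccine with a different valency from the one given.

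Patients are vaccinated and bled partly to answer this question. If staff follow the laboratory list as written, no pneumococcal titre is produced. If titres are added later, the available samples depend on which section the site followed. Under one schedule the first post-vaccine value is late, so a patient who never responded and one whose antibody has since fallen could look alike. Under the other, the comparison starts before six weeks of pembrolizumab, so a change in titre cannot be tied to the vaccine alone.

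**Working it through.** **1. The plan's own figure.** Inputs from 4.1: null 0.40, alternative 0.60, 25 patients, power 90%. No alpha is given for this hypothesis; I take one-sided 0.05 to 0.10 as an assumption. With X binomial (25, p), alpha = P(X ≥ r | 0.40) and power = P(X ≥ r | 0.60):

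| Responders required | Alpha | Power |
|---|---|---|
| ≥ 12 | 0.268 | 0.922 |
| ≥ 14 | 0.078 | 0.732 |
| ≥ 15 | 0.034 | 0.586 |

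The stated 90% does not reproduce with 25 patients at alpha of 0.10 or less. An exact single-stage test needs 41 patients at one-sided 0.10, or 56 at 0.05. The 25 comes from the complete response design in 10.2.1, which does reproduce: alpha 0.095, power 0.903, expected sample size 20.37, early termination probability 0.515 (stated as 0.52). The power gap is a separate matter and the present point does not depend on it.

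**2. Assay against endpoint.** The endpoint needs a count of antigens with a detectable antibody response.

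| Item in the 4.1 laboratory list | Gives a per-antigen pneumococcal result? |
|---|---|
| Cytokine panel | No |
| T-cell flow cytometry | No |
| Total immunoglobulins, IgG subtypes | No; not specific to any antigen |
| Fc-receptor patterns | No |
| Minimal residual disease | No |
| Stored DNA and RNA | No |

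**3. Sampling against vaccination.** Interval = sample week − 6.

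| Source | Last sample before vaccine | First samples after vaccine |
|---|---|---|
| 7.1.13, 7.3.2, footnote 12 | Week 6 | Week 21: 21 − 6 = 15 weeks |
| 7.2 | Baseline, 6 weeks before | Week 9: 9 − 6 = 3 weeks; week 12: 12 − 6 = 6 weeks |

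Section 7.1.13 makes the week 6 draw pre-dose, and 7.3.2.4 lists it before the vaccine, so I read it as pre-vaccine. The remaining sample, at end of ibrutinib, falls 48 weeks after the vaccine if that is study week 54 (last dispensing at week 51 plus 3 weeks, 7.3.7 footnote 2). It falls 54 weeks after if 4.1's 54 weeks of ibrutinib are counted from week 6 (6 + 54 = 60; 60 − 6 = 54). It is late either way. The first schedule has the right starting sample without an early follow-up; the second has early follow-ups without the right starting sample.

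**4. Responder threshold.** Section 4.1 refers to a 7-valent vaccine and 7.7 to Prevnar 13. More than 6 antigens means all 7 of 7 for the first, but at least 7 of 13 (7/13 = 54%) for the second. The same words set two very different bars.

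**5. Prior-vaccination rules.** Counting week 6 as day 42, 8 weeks earlier is day 42 − 56 = −14. From day −14 to the start of treatment, criterion 15 should already have excluded the patient. From the start to day 42, the 7.7 condition reaches only someone vaccinated off schedule, before ibrutinib begins. The 4.1 hypothesis concerns vaccination in the context of both agents, so neither patient fits it.

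**The case against.** Several replies have force.

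- **The reference is to Section 4.1 as a whole.** That section contains the hypothesis on antibody responses, Section 3 names titres, and 7.7 says Prevnar 13 is used to evaluate immunogenicity. The intention is clear. But the hypothesis text names no assay, detection threshold, specimen or time point, so the intention has no procedure behind it.
- **Part of the 10.1 endpoint is covered.** Section 10.1 also describes the vaccine response through T-cell subsets and cytokines, which are in the laboratory list. This stands: only the antibody component lacks an assay.
- **The tier is low in places.** Titres are exploratory in Section 3 and absent from 4.2.2. This stands and limits the weight of the point, but 4.1 and 10.1 say secondary.
- **The two prior-vaccination rules overlap rather than clash.** Largely true: before treatment starts, the 7.7 condition is redundant. They still need one consistent reading.

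Three stronger readings are tempting and are not supported:

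- A reader of the schedule of events might infer that nothing is drawn between week 6 and week 21. Section 7.2 lists weeks 9 and 12, so the defect is a contradiction, not an absence.
- A reader might infer that the timing makes the endpoint unmeasurable. Weeks 6 and 21 form a before/after pair, though a late one, and 7.2 keeps plasma for the duration of the trial, so titres could be added.
- A reader might infer a known loss of responders through waning by week 21. The documents give no waning figure. Any estimate would be an assumption, and would apply only to the week 21 schedule.

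**Conclusion.** The point holds in this form: none of the listed laboratory assays gives a pneumococcal antibody result, although 4.1 states a hypothesis on one, and 10.2.2 has no responder analysis to receive it. The sampling sections contradict each other. Neither version pairs a week 6 pre-vaccine sample with an early post-vaccine sample: the first follow-up is either 15 weeks after the vaccine, or 3 and 6 weeks after it with only a baseline taken six weeks before it.

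The conclusion rests on reading the 4.1 laboratory list as the list of tests to run, as 7.2 and footnote 12 direct, and on vaccination at week 6. It does not rest on any assumed rate of waning. The change should be made, but it does not touch the primary complete response design. How far a late or mismatched pair would bias the response rate cannot be put in numbers from the documents.

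**What to change.** 1. Add serotype-specific anti-pneumococcal antibody titres to the laboratory list in 4.1.
2. Reconcile 7.2 with 7.1.13, 7.3.2 and footnote 12 in one sampling schedule. For this endpoint it should hold a week 6 draw stated to precede the vaccine, one early post-vaccine draw at week 9 or week 12 (both named in 7.2, and both visits already take blood), and week 21 for persistence.
3. Define response relative to the week 6 titre. Reconcile the 7-valent wording in 4.1 with Prevnar 13 in 7.7, so that the antigen count has a clear denominator.
4. State one tier for the endpoint across Sections 3, 4.1, 4.2 and 10.1, and add the matching responder analysis to Section 10.2.
5. Reconcile the 8-week provision in 7.7 with exclusion criterion 15. Report any patient not vaccinated at week 6 separately from the vaccine-response analysis.

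The cost is protocol wording, one extra tube at an existing blood draw, and the price of an assay that the objective already implies.
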